2.4.3 Primary Endpoints

1. Tumor response (modified RECIST criteria) at 1 month as shown by contrast enhanced CT/MRI. (Note: Tumor response will be determined on a per-treated lesion basis.)
2. Local recurrence rate (LRR) at 6 months as shown by contrast enhanced CT/MRI
3. Absolute Tumor enhancing maximum diameter at 1M and 6M.

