3.5.2 Inclusion Criteria

1. Patients aged 18 years or older with the diagnosis of HCC currently being evaluated for liver transplantation and considered for downstaging.
2. Patients undergoing Surefire DEB-TACE procedure as clinically determined to be part of their standard of care treatment plan.

² In order to test the hypothesis (section 2.4), this prospective study has been designed for eligible participants to receive DEB-TACE with the Surefire Precision Infusion System. Historical matched patients, who previously underwent the DEB-TACE using a standard endhole catheter, will serve as the control group for this study (section 3.1). Given the lack of available comparator data, it is most appropriate to gather the data single arm and with the data develop an appropriate statistical framework for comparison.

3. Meets Milan criteria: a single tumor that is < 5cm or a maximum of 3 tumors with each tumor <3cm AND/OR meets UCSF criteria: a single tumor that is < 6.5 cm in diameter or 2 lesions < 4.5cm with total tumor diameter <8 cm AND/OR is outside of both Milan and UCSF criteria and is being evaluated for downstaging.
4. No portal invasion or extrahepatic spread.
5. No previous chemotherapy, radiotherapy or transarterial embolization (with or without chemotherapy).
6. Eastern Cooperative Oncology Group (ECOG) performance status of 0 or 1.
7. Preserved liver function (Child-Pugh Class A or B).

3.5.3 Exclusion Criteria:

1. Advanced bilirubin levels > 3 mg/dl
2. INR > 2 in the absence of anticoagulation therapy
3. AST or ALT>5 upper limit of normal or >250 U/l
4. Advanced tumoral disease, defined as vascular invasion, extrahepatic spread, or diffuse HCC (50% liver involvement)
5. Contraindications for doxorubicin administration.
6. Child's Class C

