For the outcome of tumor response measured as the change in enhancing tumor size (pretreatment – post treatment) we will evaluate changes at 1 month and 6 month separately. We will calculate the difference in tumor enhancement size at 1 month and 6 months using enhancement size at initial treatment as the reference group (i.e. we will have two continuous outcomes which can be positive or negative values). The analyses are exactly parallel for 1 month and 6 month outcomes. We will describe the approach for 6 months. We will fit a general linear model with Kenward-Roger denominator degrees of freedom. The outcome will be the first-differenced 6 month tumor enhancement size. We will use a random intercept to account for correlation between lesions within a given patient. The independent variables will include catheter type, age and sex. We will test the null hypothesis of no association between catheter type and change in tumor enhancement size. In the case that this model fails to converge, or in the case that most patients have only one tumor, we will use an alternative approach. In this alternative approach we will sample one lesion per patient and use ordinary least squares regression and include age and sex as covariates with catheter type as the primary predictor of interest. We will test the null hypothesis of no association between change in tumor enhancement size and catheter type. Should this model also fail to converge, we will simplify further and use a paired t-test comparing initial and 6 month tumor enhancement sizes in a sampled data set (i.e. one tumor per patient), or we will use a Wilcoxon-Mann-Whitney test if the sizes are skewed. We will test the null hypothesis of no association between catheter and tumor enhancement size change.

For the outcome of time to progression, we will quantify the number of weeks from treatment until tumor progression. Failures (or events) will be defined as progression of the tumor per CT examination or AFP level and extrahepatic disease by CT examination, or death due to complications related to the tumor. Censored observations will be defined as patients who we did not observe tumor progression, patients who were lost to follow up, or patients who had a

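### The SAP drops its all-lesion mixed model whenever most patients have one tumour and analyses one sampled lesion per patient, with no statistical reason and no rule for the draw

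*Combined protocol and SAP*

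**What the plan says.** Section 4.4 analyses the change in enhancing tumour size at 1 and 6 months, separately, by a linear model with catheter type, age and sex. On lesions within patients it states: "We will use a random intercept to account for correlation between lesions within a given patient".

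Two conditions lead away from that model. One is non-convergence. The other is "or in the case that most patients have only one tumor, we will use an alternative approach". They are joined by an or, so the second applies even to a model that has converged. The alternative is then: "we will sample one lesion per patient and use ordinary least squares regression and include age and sex as covariates". The last fallback in the same paragraph also works on one sampled tumour per patient.

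The documents do not say how the lesion is chosen, what seed is used, how many draws are made, or whether the same lesion serves both time points. They give no cut-off for the single-tumour condition and plan no all-lesion sensitivity analysis.

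Section 2.4.3 lists as its third primary endpoint "Absolute Tumor enhancing maximum diameter at 1M and 6M" (the summary in section 1.2 names only the first two). For tumour response, section 2.4.3 notes: "Tumor response will be determined on a per-treated lesion basis". Section 3.5.2 admits patients with several tumours: its Milan option allows "a maximum of 3 tumors with each tumor <3cm", and patients outside both Milan and UCSF criteria are also eligible.

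**The concern.** Having many patients with one lesion is no reason to delete the additional lesions of the others. A random-intercept model takes patients with one lesion and patients with several together. Single-lesion patients inform the catheter comparison, and multi-lesion patients also inform the within-patient correlation. The condition therefore replaces a working analysis with one that uses less data, on an endpoint that section 2.4.3 calls primary and for a response that it assesses lesion by lesion.

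Two things are at stake. The first is precision. The second is reproducibility: two analysts following the plan on the same data can draw different lesions and report different estimates and p-values, and nothing in the text says which draw counts. If the word sample is not meant as random sampling, the selection is simply undefined.

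**Working it through.** **A figure to reproduce.** The plan gives no power or precision figure for this model. Its only power table (section 4.3) concerns local recurrence and does not bear on this point.

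**Inputs.** From section 3.3: 50 device patients and 100 controls. Not in the documents, so assumed: the shares of patients with 1, 2 and 3 lesions, and the intraclass correlation (ICC) between lesions of one patient. The lesion distribution and ICC are taken to be the same in both groups, so that the ratios below carry over to the catheter effect. The 50% mix is the limiting case of a majority.

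**Step 1: efficient all-lesion analysis (mixed model or exchangeable GEE) against one lesion.** A patient with m lesions contributes information m/(1 + (m-1)·ICC), and one sampled lesion contributes 1. Relative information R is the mean of the first over patients. The confidence interval from one sampled lesion is wider by the factor √R.

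| Shares with 1/2/3 lesions | ICC | R | √R |
|---|---|---|---|
| 0.7/0.2/0.1 | 0.2 | 0.7 + 0.2·(2/1.2) + 0.1·(3/1.4) = 1.25 | 1.12 |
| 0.7/0.2/0.1 | 0.6 | 0.7 + 0.2·(2/1.6) + 0.1·(3/2.2) = 1.09 | 1.04 |
| 0.5/0.3/0.2 | 0.2 | 0.5 + 0.3·(2/1.2) + 0.2·(3/1.4) = 1.43 | 1.20 |
| 0.5/0.3/0.2 | 0.6 | 0.5 + 0.3·(2/1.6) + 0.2·(3/2.2) = 1.15 | 1.07 |
| 0.9/0.05/0.05 | 0.2 | 0.9 + 0.05·(2/1.2) + 0.05·(3/1.4) = 1.090 | 1.044 |
| 0.9/0.05/0.05 | 0.6 | 0.9 + 0.05·(2/1.6) + 0.05·(3/2.2) = 1.031 | 1.015 |

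**Step 2: unweighted OLS on all lesions with patient-clustered standard errors.** Relative information is (mean m)² / mean[m(1 + (m-1)·ICC)].

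- 0.7/0.2/0.1, mean m = 1.4: 1.96/1.60 = 1.225 at ICC 0.2; 1.96/2.00 = 0.98 at ICC 0.6.
- 0.5/0.3/0.2, mean m = 1.7: 2.89/2.06 = 1.40 at ICC 0.2; 2.89/2.78 = 1.04 at ICC 0.6.

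So the choice of replacement matters: unweighted OLS can be slightly less precise than one sampled lesion.

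**Step 3: dependence on the draw.** A simulation used 100 and 50 patients, 51-90% with one lesion and the rest split equally between two and three, ICC 0.2-0.8, and an assumed true effect of 0.4 outcome SDs. It ran 60 data sets per scenario and 200 one-lesion draws per data set. The comparator was all-lesion generalised least squares at the known ICC.

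- Lesions dropped: about 22 to 110, or 13% to 42% of all lesions.
- Variance ratio, one lesion over all lesions: about 1.0 to 1.4, in line with Step 1.
- SD of the catheter estimate across draws from the same data: 0.02 to 0.08 outcome SDs, which is 11% to 48% of its standard error.
- Share of data sets in which significance at 0.05 depended on the draw (5-95% of draws significant): roughly 17% to 58%.

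The last figure is specific to the assumed effect. With a standard error near 0.175, 0.4/0.175 ≈ 2.3, close to the threshold, where reversals are most frequent.

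**The case against.** One observation per patient is a simple and valid way to remove clustering. It weights patients equally, whereas unweighted OLS on all lesions gives a three-lesion patient three times the weight. If lesion count is related to response, the two answer different questions. If nearly all patients have one tumour, little is lost. The sample size rests on local recurrence, section 4.3 calls the study a pilot, and section 3.4 records that it closed on June 18, 2018. On this view it would be enough to define the condition and fix a selection rule and seed.

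Much of this stands, and it limits the point. It does not justify the condition. The plan's own main model already uses all lesions with its own weighting of patients, and nothing in section 4.4 says that equal weighting is the aim. Closure stops data collection but does not settle how collected data are analysed, and section 4.3 intends these data for planning a multicentre trial.

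Four stronger readings are tempting and not supported:

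- *The sampled analysis is biased or inflates type I error.* A single random draw does neither. The missing seed leaves room to redraw, but nothing in the documents suggests that this is intended.
- *The condition is likely to be met.* No section gives lesions per patient, and eligibility extends to multi-tumour patients outside Milan and UCSF.
- *Draw variability comes on top of the wider interval.* The variance of the one-lesion estimator already contains it.
- *Any all-lesion analysis would be more precise.* Step 2 shows otherwise for unweighted OLS.

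**Conclusion.** The concern holds in a limited form. Section 4.4 can discard a converged all-lesion model, and with it treated lesions, on a condition that has no statistical basis and no cut-off. It then reports an estimate that depends on an unspecified draw. The cost is precision and reproducibility, not validity.

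Relative to the mixed model or exchangeable GEE, the confidence interval is about 4-20% wider if 50-70% of patients have one lesion and the ICC is 0.2-0.6, and about 1.5-4.4% wider if 90% have one lesion. These figures rest entirely on assumed lesion counts and correlations. The point is minor in size, but it is clear on the text and cheap to correct.

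**What to change.** Delete the single-tumour condition from section 4.4 and keep the all-lesion random-intercept model whatever the share of single-lesion patients. Only if that model fails to converge, use GEE with an exchangeable working correlation on all treated lesions, with catheter type, age and sex, and small-sample-corrected standard errors clustered by patient. Remove or reword the last fallback, which also relies on sampled lesions.

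Unweighted OLS with clustered standard errors would be valid, but it may gain no precision at high ICC and weights multi-lesion patients more heavily, so it is not the preferred fallback. If sampling is kept for any purpose, state the rule and seed in advance, use the same lesion at 1 and 6 months, and average over many draws.

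The cost is SAP wording only: no additional data, patients or assessments.

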3.3 Sample Size

Fifty (50) subjects will be enrolled in the prospective arm.

Data from one hundred (100) historical randomly sampled control subjects (1:2 ratio) will be selected.

The statistical basis for the sample size is provided in Section 4.3.

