4.4 Statistical Analysis Plan

All statistical tests use a type I error rate of 0.05. We will calculate descriptive statistics for all variables of interest including means, medians and standard deviations for continuous measures, and frequencies and percents for categorical variables. These calculations will be performed overall and stratified by treatment assignment. We will compare baseline characteristics between the treatment and retrospective groups. We will test for differences using independent samples t-tests (alternatively, Wilcoxon-Mann-Whitney tests if data are skewed) for continuous variables, and Chi-square tests (alternatively Fisher's exact tests if some cells are sparse) for categorical variables.

For the outcome of local recurrence rate (LRR) we will test the null hypothesis of no difference in the proportion of patients with local recurrence by catheter type using a Fisher's exact test.

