liver transplant before evidence of progression was found. For censored observations the time at risk will be calculated as the time from treatment initiation to the last known clinical encounter (for no progression or lost to follow up), or to liver transplant (for patients who had a liver transplant before evidence of progression was found); this will be measured in weeks. To test for differences in time to tumor progression between the treatment and the retrospective group, we will use Cox proportional hazards regression. Treatment group will be our primary predictor of interest, and we will include age, sex and a variable approximating stage/severity at time of treatment using homogenous groups. We will test the null hypothesis of no association between time to progression and treatment group.

For the outcome of survival time, we will quantify the number of weeks from treatment until death. Failures (or events) will be defined as death related to the tumor. Censored observations will be defined as patients who we did not die during the follow up period, or patients who were lost to follow up. For censored observations the time at risk will be calculated as the time from treatment initiation to the last known clinical encounter; this will be measured in weeks. To test for differences in survival time between the treatment and the control group, we will use Cox proportional hazards regression. Treatment group will be our primary predictor of interest, and we will include age, sex and a variable approximating stage/severity at time of treatment using homogenous groups. We will test the null hypothesis of no association between survival time and treatment group.

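### The survival analysis counts only tumour-related deaths as events and leaves known deaths from other causes unclassified, so it does not measure survival as labelled

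*Combined protocol and SAP*

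**What the plan says.** The survival paragraph of Section 4.4 (Statistical Analysis Plan) makes four statements.

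- Outcome: "we will quantify the number of weeks from treatment until death". No cause is attached.
- Event: "Failures (or events) will be defined as death related to the tumor".
- Censoring: "Censored observations will be defined as patients who we did not die during the follow up period, or patients who were lost to follow up". Their time at risk is "calculated as the time from treatment initiation to the last known clinical encounter; this will be measured in weeks".
- Test: "To test for differences in survival time between the treatment and the control group, we will use Cox proportional hazards regression", adjusted for age, sex and a stage/severity variable. The null is no association between survival time and treatment group. The same section sets the level: "All statistical tests use a type I error rate of 0.05".

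The comparison is between 50 prospective patients and 100 historical controls (Section 3.3). The controls come from patients treated at the same institution since 2009 (Section 2.4.1). Survival time is not among the primary endpoints (Section 2.4.3) or the secondary endpoints (Section 2.4.4).

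**The concern.** The outcome as named and the event as defined are different quantities. A reader of the results would take a survival hazard ratio to mean mortality. As written, it reflects only deaths that someone has attributed to the tumour.

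Deaths from other causes are foreseeable in this population. Patients have Child-Pugh class A or B liver function (Section 3.5.2) and receive doxorubicin-loaded beads. Section 3.12 anticipates arterial dissection, arterial thrombosis and unacceptable adverse events. A catheter comparison called survival should be able to register a fatal complication, and this one cannot.

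Two further problems follow. The plan leaves the analyst to decide how to treat these deaths after they are known. The event also depends on attribution of cause, for which the documents give no definition, adjudication or blinding. In the prospective group the judgement is made by staff who know the catheter. In the control group it comes from existing records. The fact of death is much less open to such differences.

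**Working it through.** The plan states no survival event count, hazard ratio or power, so there is no figure to reproduce. The check is of the definitions, followed by an illustration on assumed inputs.

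**Step 1: place every possible patient under the survival rule in Section 4.4.**

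| Patient status | Event? | Censored? | Time at risk given? |
|---|---|---|---|
| Tumour-related death | Yes | No | Yes, to death |
| Alive at end of follow-up | No | Yes | Yes, to last encounter |
| Lost to follow-up | No | Yes | Yes, to last encounter |
| Known death from another cause | No | No | No |

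The last row is empty.

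**Step 2: look for a rule elsewhere.**

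- The time-to-progression paragraph in Section 4.4 also counts only tumour-related death. Its censoring group, however, is patients without observed progression, which can absorb a non-tumour death. The survival group, patients who did not die, cannot. Time to progression also has a liver-transplant rule, and survival has none.
- Section 4.6 grades fatal adverse events as Grade 5 and lists death as a seriousness criterion. This is safety reporting and is not linked to the survival analysis. The same section exempts deaths from cancer progression from SAE reporting, so it does not give an all-cause count either.
- No competing-risk method and no attribution rule appear anywhere.
- The only death count is in the Section 2.4.1 tables: 2 of 77 one-month partial responders by 6 months, with no cause stated.

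**Step 3: what the two available choices do.** Let *s* be the non-tumour share of the control death hazard, *h* the tumour-death hazard ratio and *m* the non-tumour hazard ratio (study catheter over control). With constant hazards:

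all-cause HR = (1 − s)·h + s·m

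If non-tumour deaths are censored, the Cox model estimates *h*, whatever *m* is. None of *s*, *h* or *m* is in the documents, so the following values are assumptions.

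- *Case A: excess non-tumour deaths with the study catheter.* With s = 0.4, h = 1, m = 2, the all-cause HR is 0.6 × 1 + 0.4 × 2 = 1.40. Censoring gives 1.00. Excluding those patients gives 1.10 (simulation, tumour-death hazard 0.15 per year, 2 years of follow-up). Over s = 0.2 to 0.6 and m = 1.5 to 3, the all-cause HR runs from 0.8 + 0.2 × 1.5 = 1.10 to 0.4 + 0.6 × 3 = 2.20. The censored result stays at about 1.00, and the excluded result runs from 1.02 to 1.59.
- *Case B: benefit on tumour deaths only.* With s = 0.5, h = 0.60, m = 1, the all-cause HR is 0.5 × 0.60 + 0.5 × 1 = 0.80. Censoring gives 0.60.

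In both cases the tumour-only result looks better for the study catheter than all-cause mortality does. That ordering follows from assuming m > h. With m < h it reverses. The illustration shows that the definition and the handling choice matter, not how large or in which direction the effect would be here.

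**The case against.** The strongest case on the other side has four parts.

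- *Tumour-specific survival is a recognised outcome, and the usual practice would be to censor other deaths.* This stands as far as it goes: the plan does not order these patients to be excluded. A reader might infer that treatment-related and liver-failure deaths are removed from the comparison. The text leaves them unclassified, and because relatedness to the tumour is undefined, some liver-failure deaths might be judged tumour-related. But a legitimate cause-specific analysis has to be named as such and has to say what happens to the other deaths. This one does neither.
- *Fatal complications are not lost to the study.* This stands for the prospective arm. Treatment-related toxicity is a secondary endpoint (Section 2.4.4), deaths resulting from the procedure are reportable (Section 4.6), and the safety committee reviews serious events (Section 4.8). A reader might infer that such deaths can never count against a catheter. The supportable statement is narrower: they cannot count in the survival hazard ratio.
- *The loss of precision cannot be sized.* A reader might argue that if a share q of deaths is non-tumour, the standard error of the log hazard ratio rises by 1/√(1 − q), that is by 12% at q = 20% and 41% at q = 50%. The documents do not support this as a measure of harm. The share is assumed, and the formula treats two different estimands as one. In Case B, in units of the all-cause standard error, the signal is |ln 0.80| = 0.22 for all-cause death and |ln 0.60|/1.41 = 0.36 for tumour death. The analysis with fewer events has the stronger signal.
- *The consequence is limited.* This stands. Survival is not a listed endpoint, the sample size rests on local recurrence (Section 4.3), and the study closed on 18 June 2018 (Section 3.4). Closure did not withdraw the analysis: Section 4.4 still commits to an adjusted Cox model and a tested null, and Section 4.3 says the pilot data will be used to plan a multicentre trial.

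**Conclusion.** The point holds as a defect in the survival definition. The outcome is labelled as time to death, the event is tumour-related death only, and known deaths from other causes have no category and no time at risk. Under either handling, they are never failures in the Cox comparison. The event also depends on an undefined attribution of cause, made under different conditions in the two groups. These conclusions rest on the text alone and need no assumption.

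The size and direction of any bias cannot be derived from the documents. The hazard ratios in the working are illustrations. In particular, nothing in the documents shows higher non-tumour mortality with the study catheter. The issue affects an additional analysis and leaves the primary tests, the listed secondary endpoints and the stated power figures untouched. It should be corrected before a survival hazard ratio is reported or used for planning.

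**What to change.** Amend the survival paragraph of Section 4.4 as follows.

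1. Define the event as death from any cause.
2. Censor patients not known to have died at the date last known alive, in both groups.
3. State how follow-up after liver transplant is handled, identically in both groups. The population is transplant candidates, and without a rule post-transplant deaths would enter the catheter comparison undiscussed.
4. If tumour-related death is kept, call it tumour-specific survival. Report it as a cause-specific sensitivity analysis, with other deaths treated as competing events and censored at the date of death. Apply one written attribution rule to prospective and historical patients.

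The cost is SAP wording. The main survival analysis would no longer need a cause-of-death judgement. One limit remains: follow-up visits and data entry stopped on 18 June 2018, so vital status after that date would not be available under this version. All-cause death reduces the dependence on unequal ascertainment between the groups but does not remove it, because loss to follow-up can also differ.
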